- 6) H5 pseudotyped lentiviral particle-based serological assay titer assessed as the highest sample dilution that produces 50% inhibition of virus control.

7) Influenza specific T-cell cytokine production by influenza-specific T-cells defined as the percentage of cytokine-staining cells at least twice background.

8) Human monoclonal antibody production from peripheral blood memory B cells isolated from selected subjects

Duration of Subject Participation

This study will take up to 12 months from enrollment of the first subject to completion of the *in vivo* portion. Each subject will be followed up for approximately 12 weeks following entry into the study (screening, dosing, follow-up). The total study duration will be 2 years.

A subset of previously enrolled subjects may be invited to participate in an additional phase of the study, which will involve consent for use of stored sample and a possible single blood draw if extra sample is required. No follow-up will be required after the day of blood draw

Safety Data Collected

Subjects will complete a symptom diary for 14 days following each dose of vaccine. Adverse event monitoring will continue throughout the study duration.

TABLE OF CONTENTS

| I. | GENERAL INFORMATION | 9 |
|------|--|------|
| II. | INVESTIGATOR PROTOCOL AGREEMENT PAGE | 11 |
| III. | ABBREVIATIONS | 12 |
| IV. | BACKGROUND INFORMATION | 13 |
| | IV.1.INTRODUCTION | 13 |
| | IV.2. IMMUNOLOGY OF INFLUENZA AND INFLUENZA VACCINES | 13 |
| | IV.2.1. INFLUENZA VIRUS | 13 |
| | IV.2.2. AVIAN INFLUENZA H5N1 | 14 |
| | IV.2.3. IMMUNE RESPONSES TO INFLUENZA VIRUS | 15 |
| | IV.2.4. INFLUENZA VACCINES | 15 |
| | IV.2.5. LIVE ATTENUATED INFLUENZA VACCINES | 16 |
| | IV.2.6. VACCINES AGAINST AVIAN INFLUENZA H5N1 | . 16 |
| | IV.3.FLUMIST® LIVE, ATTENUATED INFLUENZA VACCINE | 18 |
| | IV.3.1. PRODUCT INFORMATION | 18 |
| | IV.3.2. SAFETY AND TOLERABILITY FOLLOWING SINGLE AND DUAL DOSE ADMINISTRATION IN HEALTHY SUBJECTS | 19 |
| | IV.3.3. SAFETY IN SPECIAL GROUPS | 20 |
| | IV.3.4. SECONDARY TRANSMISSION OF VACCINE VIRUS | 21 |
| | IV.4. FLUZONE® INFLUENZA VACCINE | 22 |
| | IV.4.1. PRODUCT INFORMATION | 22 |
| | IV.4.2. SAFETY AND TOLERABILITY FOLLOWING SINGLE AND DUAL DOSE ADMINISTRATION IN HEALTHY SUBJECTS | 22 |
| | IV.4.3. SAFETY IN SPECIAL GROUPS | 23 |
| | IV.5. CONCOMITANT ADMINISTRATION OF FLUMIST® AND FLUZONE® | 23 |
| | IV.6.STUDY JUSTIFICATION | 24 |

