In general, immune responses to vaccines can be increased by 1 of 3 ways: addition of adjuvant and/or administration of multiple doses and/or a combination of 2 different vaccine strategies (heterologous prime-boost). Since H5N1 is antigenically diverse from current human influenza, it is expected that a different strategy will be needed to induce protective immune responses as compared to seasonal influenza. Indeed, multiple doses were required for all candidate H5N1 vaccines or vaccines that induce cross-protection tested so far and most candidate H5N1 vaccines were poorly immunogenic without adjuvant (Subbarao, 2007). Alternatively or additionally, two diverse vaccines could be used sequentially in a so-called heterologous prime-boost strategy to increase and broaden immune responses. It has been well documented that heterologous prime boost vaccination elicits high-magnitide, broad-based and long-lasting immunity in several different animal and disease models {Verrier, 200} {McConkey,2003} {Gomez, 2007}. In such a primeboost vaccination, one vaccine is used to initiate immune responses ("prime"), followed by a second immunization with a different vaccine to boost immune responses. In the case of influenza, LAIV and IIV could be combined as a prime-boost vaccination. This approach has several advantages over using two immunizations with the same vaccine. Firstly, upon a 2nd immunization with LAIV memory responses will rapidly lead to elimination of the virus, thus drastically reducing viral replication, immune responses and ultimately vaccine efficacy. More importantly, we expect that by combining a mucosal vaccine containing live virus with an intramuscular vaccination using inactivated virus, induced immune responses will be broader and higher, both systemically and mucosally. Our approach, therefore, is to compare cross-reactivity of two doses of seasonal LAIV or IIV to H5N1 versus a prime/boost dosing of LAIV followed by IIV or vice versa. We hypothesize that such a

prime-boost strategy will favor generation of both IgA and IgG antibodies that are able to cross-react with and protect against H5N1.

IV.3. FluMist[®] Live Attenuated Influenza Vaccine

IV.3.1. Product information

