Because of the difficulties encountered in producing a specific H5N1 vaccine, and the animal data showing appreciable cross-protection of LAIV with other influenza A viruses, this study will contribute significantly to our understanding of human immune cross-protection to H5N1 following single, dual or prime boost vaccination with currently available seasonal influenza vaccines. The dosing regimes proposed here for healthy adults are designed to achieve the maximal immune response so that the chance of detecting any measurable cross-protection is maximized. Although safety data on dual dosing with influenza vaccine in healthy adults is limited, the available data from children and adults with chronic medical conditions do not suggest there will be significant additional risks from the second dose.

IV.7. Additional Background Information and Justification for Amendment 6

Memory B cells are known to persist for a lifetime and therefore represent an ideal repository for antibody specificities generated by an individual after vaccination (Lanzavecchia, 2009). Unlike plasma cells, memory B cells can be immortalized by Epstein Barr virus (EBV). The EBV-transformed memory B cells produce large amount of antibodies; however the efficiency of B cell immortalization and cloning is low. An improved method of EBV immortalization has now been established using the TLR9 ligand CpG ODN, which is able to enhance the efficiency of EBV B-cell immortalization more than 100-fold (Traggiai, 2004). This method has been employed to dissect the human antibody response to pathogens such as, SARS (Traggiai, 2004), avian influenza H5N1 (Simmons, 2007), HIV (Corti, 2010), and dengue (Beltramello, 2010).

Preliminary analysis of data from WRAIR #1525 indicates that serum from a subset of subjects exhibited potent *in vitro* cross-reactivity to H5N1 and pandemic H1N1 2009. The observed antibodies are probably generated from long-lived, cross-reactive memory B cells produced in response to a prime-boost vaccination with seasonal influenza vaccine, since it is likely that these subjects had never previously been exposed to H5N1 and/or pandemic H1N1 2009.

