We propose to attempt to produce human monoclonal antibodies from the original samples collected from those subjects with high responses to allow for further analysis of the immune response to influenza vaccines. Subjects will be re-contacted to assess willingness to participate in an additional blood sampling under a minimal-risk human use protocol. A greater understanding of cross-reactive memory B cell responses to influenza neuraminidase and hemagglutinin may eventually lead to new/novel preventive and therapeutic strategies.

V. OBJECTIVES

The hypothesis to be tested in this study is that heterologous prime-boost vaccination of healthy adults with a prime boost regimen of trivalent LAIV (FluMist®) and trivalent IIV (Fluzone®) will induce cross-immunity to a variety of H5N1 avian influenza viruses and human influenza viruses.

Therefore the primary objectives of this study are:

- 1. To establish whether a prime boost strategy using seasonal LAIV and IIV can augment cross-reactivity with H5N1 and human influenza strains.
- 2. To detect the presence of antibodies that can inhibit infection with H5N1 and human influenza strains in microneutralization, plaque reduction, or H5 pseudotyped lentiviral particle-based assays after vaccination with seasonal LAIV and IIV.
- 3. To establish the breadth of antibody responses to H5N1 strains and human influenza strains using ELISA, microneutralization, plaque reduction, H5 pseudotyped lentiviral particlebased assays, neuraminidase inhibition assay, and hemagglutination inhibition after vaccination with seasonal LAIV and IIV.
- 4. To observe T-cell responses following vaccination with seasonal LAIV and IIV.
- 5. To attempt to generate human monoclonal antibodies that are cross-reactive to enzyme neuraminidase and hemagglutinin of H5N1 and pandemic H1N1 2009 in order to investigate further the human response to influenza vaccination

Secondary objectives are to describe the adverse event profile of 2 doses of influenza vaccine given approximately 8 weeks apart in healthy adult volunteers.

VI. METHODS

VI.1. Study Endpoints

The primary study endpoints will be determination of pre and post vaccination immune responses in 26 healthy human subjects to 2 doses of seasonal influenza vaccine including whether there is *in vitro* cross-reactivity against H5N1 virus as follows:

- 1. Antibodies ELISA titers calculated as the dilution factor required to give an optical density of 0.5.

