- 2. Hemagglutination inhibition activity defined as the titer required to completely inhibit hemagglutination);
- Microneutralization assay endpoint titer; determined by using 50% specific signal calculation. The endpoint titer will be expressed as the reciprocal of the highest dilution of serum with A490 value less than X, where X = [(average A490 of VC wells) – (average A490 of CC wells)] / 2 + (average A490 of CC wells).
- 4. Neuraminidase inhibition assay titer defined as the highest sample dilution that produces 50% inhibition of virus control.
- 5. Plaque reduction assay titer assessed as the highest sample dilution that will give a reduction of plaque count of 50%.
- 6. H5 pseudotyped lentiviral particle-based serological assay titer assessed as the highest sample dilution that produces 50% inhibition of virus control.
- 7. Influenza specific T-cell cytokine production by influenza-specific T-cells defined as the the percentage of cytokine-staining cells at least twice background.
- 8. Antibody staining against matrix 2 protein (M2e) expressed cell line. The samples considered positive are those in which the staining intensity is at least twice that for the background.
- 9. Human monoclonal antibody production from peripheral blood memory B cells isolated from selected subjects

VI.2. Study Design

This will be a randomized, open-label, pilot feasibility study of four 2-dose vaccine regimens using two commercially available seasonal influenza vaccines. The *in vivo* phase of the study will entail randomization of up to 26 adult volunteers to receive: either 2 doses of LAIV (5 subjects) (Autologous prime boost regimen 1), 2 doses of IIV (5 subjects) (Autologous prime boost regimen 2), one dose of LAIV followed by one dose of IIV (8 subjects) (Heterologous prime boost regimen 1) or one dose of IIV followed by one dose of LAIV (8 subjects) (Heterologous prime boost regimen 2) (Appendix 2). AE data will be collected into a symptom diary for 14 days following each dose of vaccine. Serum and local (nasal) immunological responses will be evaluated 2 and 4 weeks after each dose. A further 8 subjects will be recruited to act as replacements in case of drop-outs.

VI.3. Study Site

The *in vivo* phase of the study will take place at the U.S. Embassy Medical Unit, Bangkok, Thailand. In selected cases individuals may elect to have scheduled follow-up visits (which do not involve vaccination) performed at AFRIMS. Immunology testing will be done at the

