T cell responses will be assessed by intracellular cytokine staining (ICS). Peripheral blood mononuclear cells (PBMC) will be isolated from blood using density gradient centrifugation as described {Thitithanyanont, 2007}. PBMC (10⁶ cells) in 200ul will be cultured in 96 wells plates with stimulatory antigens (peptide pool or viral proteins from H5N1 virus, human seasonal influenza virus, or swine flu H1N1 2009). All peptide-or protein-stimulated PBMC cultures will contain 1 ug/ml of anti-CD28 and 1 ug/ml of anti-CD49. Staphylococcal enterotoxin B and media control will be used as positive and negative controls, respectively. After the initial 2 h of stimulation, Golgiplug will be added to inhibit cytokine secretion. After 18-20 h of incubation, cells will be washed and stained for CD4 and CD8. The stained cells will be washed and treated with fixation/permeabilization solution and then stain with antibodies against IFN-g and IL-2. Isotype-match control antibody will be used to confirm the staining specificity. The stained cells will be analyzed by 4-color FACS. Approximately 200,000 to 400,000 events in the lymphocyte gate will be acquired. The samples considered positive will be those in which the percentage of cytokine-staining cells is at least twice that for the background or in which there is a distinct population of brightly cytokine-positive cells. The CD4 T cell population will be analyzed by excluding CD8 T cells, and vice versa for analysis of the CD8 T cell population. The ICS assay will be conducted at Immunology BSL2 lab, AFRIMS.

VI.10.2.9. Antibody staining against matrix 2 protein (M2e) expressed cell line

HEK 293 stably expressing M2e on the cell surface will be stained with a 1: 10 dilution of sera samples and then detected by florescent dye conjugated anti-human antibodies. Stained cells will be analyzed by flow cytometry.

VI.10.2.10. Monoclonal antibody production

Peripheral blood memory B cells from selected subjects will be isolated using a fluorescence-activated cell sorter in a BSL2 laboratory. These isolated B cells will be immortalized with EBV in the presence of TLR 9 ligand CpG ODN. The resulting antibodies produced by the immortalized B cells will be screened for neutralizing antibodies against neuraminidase and hemagglutinin of H5N1 and pandemic H1N1 2009. Positive cultures will then be cloned by limiting dilution.

VI.11. Stopping Rules

There will be no interim analysis and therefore no stopping rules for this study.

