In addition there will be an in-house study monitor assigned to this study to ensure compliance with GCP/ICH standards. Monitoring will consist of a pre-study site visit, regular monitoring visits and a post-study visit.

XII. STATISTICAL METHODS

XII.1. Sample Size and Power

This is a descriptive study designed to detect trends in safety and immune responses that would warrant expanded investigations of potentially promising combinations {Lancaster, 2004} {Browne, 1995}. The sample size of 8 subjects in arms 3 and 4 and 5 in arms 1 and 2 is in the range of what is considered adequate for phase I trails and is not based on sample size and power calculations {Stephenson, 2005} {Lin, 2006} {Nicholson, 2001}.

Recruitment of subjects is likely to be affected by the limited number of US citizens resident in Bangkok who fulfill the eligibility criteria. Hence there will be no stratification of enrolment based on gender; this and other possible confounders (such as prior receipt of influenza vaccines) can be addressed in future large-scale trials.

XII.2. Study Outcome Analysis

Primary Analysis

Immunological data and other continuous variables will be expressed as geometric means and standard deviations if the data are normally distributed, and the vaccine groups compared using parametric tests. If not normally distributed they will be expressed as medians and the range and interquartile range given; comparison between groups will then be by non-parametric tests.

Secondary Analyses

In vivo (AE) data will be analyzed as follows: categorical data will be presented using counts and percentages, whilst continuous variables will be presented using the mean, (standard deviation) or median (range and interquartile range), and number of subjects. Percentages will be rounded to a maximum of one decimal place. All statistical tests will be performed using a 5% significance level, leading to 95% confidence intervals. Differences in incidence of reported AEs between doses and vaccines will be determined. Statistical analyses will be carried out in-house using Stata 10.0 (College Station, Texas).

XIII. ETHICAL CONSIDERATIONS

XIII.1. Study Approval

Scientific approval for this study will be obtained from the Scientific Review Committee at AFRIMS. Ethical approval will be sought from the WRAIR IRB (FWA 00000015) and the USAMRMC ORP HRPO. This study will be governed by ICH GCP guidelines.

XIII.2. Risks and Benefits of Participating

Benefits

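### XII.2 names only a generic comparison of four groups of 5, 5, 8 and 8, leaving unstated the pooled contrasts that the design supports and Objective 1 needs; the primary endpoint list and VI.11 also need reconciling

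*Protocol*

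**What the plan says.** **Comparison.** Section IV.2.6 gives the approach: to "compare cross-reactivity of two doses of seasonal LAIV or IIV to H5N1 versus a prime/boost dosing of LAIV followed by IIV or vice versa". Objective 1 asks whether prime boost can augment cross-reactivity, without naming a comparator. The arms are labelled autologous (1 and 2) and heterologous (3 and 4).

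**Analysis.** XII.2 compares the vaccine groups by parametric or non-parametric tests and names no contrast. Under Secondary Analyses it adds: "All statistical tests will be performed using a 5% significance level, leading to 95% confidence intervals". XII.1 calls the study descriptive and unpowered: "The sample size of 8 subjects in arms 3 and 4 and 5 in arms 1 and 2 is in the range" considered adequate for a phase I trial.

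**Endpoints.** The Study Summary lists eight primary endpoints and VI.1 lists nine. The extra one in VI.1 is "Antibody staining against matrix 2 protein (M2e) expressed cell line". Both lists end with "Human monoclonal antibody production from peripheral blood memory B cells isolated from selected subjects".

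**Data look.** IV.7 justifies Amendment 6 with a finding from this study: "Preliminary analysis of data from WRAIR #1525 indicates that serum from a subset of subjects exhibited potent" in vitro cross-reactivity. It then proposes monoclonal-antibody work on samples from the subjects with high responses. VI.11 says: "There will be no interim analysis and therefore no stopping rules for this study".

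**The concern.** The regimens are formed by first vaccine and second vaccine, LAIV or IIV each time. That structure allows arms to be combined in two useful ways, and XII.2 mentions neither. If the four groups are simply compared with one another, the first-dose data are split between arms that have not yet been treated differently. The heterologous-versus-autologous comparison announced in IV.2.6 is then reached only through separate comparisons of 8 with 5.

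XII.1 says that the results are to identify promising combinations for larger studies. Imprecise arm-by-arm comparisons across many assays, each read at 5%, can put the wrong regimen forward.

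The endpoint list adds a separate problem. An item measured only in subjects chosen for their response cannot compare randomised arms, yet it is called primary. The two lists disagree, and VI.11 does not acknowledge the analysis on which IV.7 relies.

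**Working it through.** **Inputs.** Planned arm sizes are 5, 5, 8 and 8 (XII.1), which sum to 26 as stated. There is no power calculation to reproduce, and the protocol gives no SD or effect size. Standard errors are therefore in units of the between-subject SD on the log-titre scale, taken as equal across arms.

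**1. Which arms share treatment, and until when.** Arms 1 and 3 both start with LAIV; arms 2 and 4 both start with IIV. The second dose is given at Day 56, and the table of volunteer assessments marks the Day 56 blood and nasal wash as taken before vaccination. So Days 14, 28 and 56 all precede any difference within each pair: LAIV first 5 + 8 = 13, IIV first 5 + 8 = 13. Cells for the T-cell assay are drawn only on Days 0, 14 and 70, so for that assay only Day 14 applies.

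**2. Precision.** SE = √(1/n₁ + 1/n₂).

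| Comparison | Variance | SE (SD units) |
|---|---|---|
| Dose 1, arm 1 v arm 2 (5 v 5) | 0.400 | 0.632 |
| Dose 1, arm 3 v arm 4 (8 v 8) | 0.250 | 0.500 |
| Dose 1, first vaccine (13 v 13) | 0.154 | 0.392 |
| After dose 2, one heterologous v one autologous arm (8 v 5) | 0.325 | 0.570 |
| After dose 2, heterologous v autologous (16 v 10) | 0.1625 | 0.403 |

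The contrast mean(arms 3, 4) minus mean(arms 1, 2) has variance ¼(1/8 + 1/8 + 1/5 + 1/5) = 0.1625, the same as 16 v 10.

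Relative information at dose 1 is 0.154/0.400 = 38% for 5 v 5 and 0.154/0.250 = 62% for 8 v 8, compared with 13 v 13. After dose 2, a single 8 v 5 comparison has 0.1625/0.325 = 50% of the information in the pooled contrast.

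**3. On the titre scale.** This needs an assumed SD of log₂ titre. The 95% interval for a ratio of geometric means is the estimate multiplied and divided by 2^(SD × t × SE), where t is the 97.5% point on n₁ + n₂ − 2 degrees of freedom.

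| Comparison | t | SD 1.0 | SD 1.5 | SD 2.0 |
|---|---|---|---|---|
| 5 v 5 | 2.306 | 2.75 | 4.56 | 7.55 |
| 8 v 8 | 2.145 | 2.10 | 3.05 | 4.42 |
| 13 v 13 | 2.064 | 1.75 | 2.32 | 3.07 |
| 8 v 5 | 2.201 | 2.39 | 3.69 | 5.69 |
| 16 v 10 | 2.064 | 1.78 | 2.38 | 3.17 |

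**4. False positives.** Monoclonal-antibody production gives no between-arm test, so VI.1 leaves 9 − 1 = 8 between-arm endpoints and the Summary leaves 8 − 1 = 7. With one test each at 5%, and independence, the chance of at least one false positive is 1 − 0.95⁸ = 33.7%, or 1 − 0.95⁷ = 30.2%. The assays are run on the same subjects and are correlated, so for one test per endpoint these are upper-end illustrations.

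**5. Endpoints and data look.** The Summary and VI.1 differ by the M2e item. The monoclonal item is limited to selected subjects, and IV.7 shows that they are selected on response after a preliminary analysis. VI.11 records no analysis before the end.

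**The case against.** The study is a declared descriptive pilot. The exact contrast, the lead strain and visit, and multiplicity handling may properly sit in an analysis plan that is not shown. XII.2 does not prescribe pairwise tests, nor does it exclude a planned contrast. This stands, and it is why the point is one of naming comparisons rather than of an invalid analysis. The same reasoning means that the choice of a single primary endpoint is a trade-off for the investigators, not a defect.

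Pooling can also hide which order is better, and IV.2.6 itself expects a second LAIV dose to do poorly, so arms 1 and 2 may differ. This stands too: the pooled contrast must accompany the separate arms, not replace them. It does not touch the first-dose comparison, where treatment within each pair is identical.

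The 5% sentence sits in the adverse-event paragraph, so its reach to the immunology data rests on the word *all*.

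Stronger readings are tempting but unsupported:

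- A reader might infer that heterologous versus autologous is the protocol's formal hypothesis. Section V begins "The hypothesis to be tested in this study is that heterologous prime-boost vaccination of healthy adults" and goes on to say that this will induce cross-immunity; it names no autologous comparator. The comparison comes from IV.2.6 and is implied by Objective 1.
- A reader might multiply nine endpoints by six pairwise comparisons and quote a 94% false-positive chance (1 − 0.95⁵⁴). That treats tests which share arms as independent, and counts an endpoint with no between-arm test.
- A reader might claim that rank tests could never pass a correction for 54 tests (0.05/54 = 0.00093). For 8 v 8 the smallest exact two-sided p is 2/12,870 = 0.00016, so they could.
- A reader might suppose that every endpoint covers all strains, sample types and visits. The T-cell assay has fewer visits, and the pseudoparticle and M2e assays use serum only.
- A reader might suspect a concealed interim analysis. IV.7 discloses the look openly, VI.11 speaks in the context of stopping rules, and nothing shows that conduct or an arm comparison was altered.

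**Conclusion.** The point holds in a limited form. XII.2 leaves unnamed the two comparisons that use the randomised data best: 13 v 13 by first vaccine before the boost, and 16 v 10 for heterologous against autologous after it. They reduce the standard error from 0.632 or 0.500 to 0.392 SD, and from 0.570 to 0.403 SD. At an assumed log₂ SD of 1.5, the 95% interval factor after dose 2 falls from 3.69 to 2.38. These figures rest on the planned arm sizes and a common SD. The first-dose gain needs no assumption about regimens. The post-dose-2 contrast is an average over two orders and two autologous regimens that may differ.

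The figure of about 34% is an illustration under independence. In a descriptive study it limits interpretation; it is not an error in the plan.

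Three textual points stand on the protocol alone: monoclonal-antibody production is wrongly called primary, the two primary lists disagree, and VI.11 does not mention the preliminary analysis.

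**What to change.** In XII.2:

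1. Analyse Days 14, 28 and pre-boost Day 56 by first vaccine received, LAIV (arms 1 and 3, n = 13) against IIV (arms 2 and 4, n = 13), for the samples taken at each visit.
2. After dose 2, report mean(arms 3, 4) minus mean(arms 1, 2) on log titre as the between-regimen estimate for Objective 1, and show each arm separately beside it.
3. Present all other between-arm results as estimates with 95% confidence intervals, in line with the descriptive aim in XII.1.

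Elsewhere:

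4. Move monoclonal-antibody production to exploratory, with no between-arm inference.
5. Make the primary lists in the Summary and VI.1 agree on whether the M2e item belongs.
6. Amend VI.11 to record the preliminary analysis described in IV.7.

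The cost is wording only, with no added subjects, samples or visits. The downside is that pairwise arm results become descriptive and fewer endpoints are called primary.
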